-2. The patients will be divided into three research arms. Patients will be randomly selected for one of the groups using a random number generator between 1 and 3. There will be a "Control Group" which will receive a rectal exam while still in the operating room in the lithotomy position after the procedure. There will be a "Postoperative OR" group which will receive a B and O suppository while still in the operating room in the lithotomy position after the procedure. Finally, there will be a "Preoperative OR" group which will receive a B and O suppository after the induction of anesthesia prior to beginning the urologic procedure in the lithotomy position. The "Control Group" will receive a rectal exam in the operating room after the procedure but before extubation to simulate the effects of suppository administration so that we know that any effects are due to the medication and not to the placement of the suppository itself. Those patients in the "control group" may receive a B and O suppository as part of standard procedure in the post-operative period if these individuals experience any bladder spasms and wish to have this as a treatment. This administration will be at the discretion of the operating surgeon as it is in standard cases. Patients may also receive Ditropan in the post-operative setting, which is part of the standard procedure for treating bladder spasms following urologic procedures. Patients in the postoperative and preoperative OR groups will be offered Ditropan for any bladder spasms in the post-operative setting to control symptoms, which is part of the normal standard of care for anyone who has already received a B and O suppository with inadequate control of symptoms. All patients will be treated with a normal post-operative pain regimen which may include narcotics. This will be at the discretion of the treating physician.

-3. In the post-operative setting, all subjects will be given a quick survey within 24 hours to assess their amount of discomfort related to bladder spasms/urinary discomfort. In addition, subjects medical charts will be reviewed to determine the amount of antimuscarinics that the patient received 24 hours post-operatively and the amount of narcotic and non-narcotic pain medication that subjects required. Patients not in the experimental arm will be given oral anti-muscarinics to treat any bladder spasms that they may have, but will not be given suppositories.

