-4. Data will be entered into the database following the procedure as available.

-5. Subjects will have clinically appropriate follow-up per the attending urologist. If, as part of that follow-up, clinically relevant events occur, the corresponding data will be recorded in the database.

Note that, with the exception of which particular study arm the subjects are enrolled into and the recording of data as detailed above and below, there will be absolutely

no difference in the care received by patients choosing to participate in this study and those who elect not to participate.

Data will be analyzed using commercially available statistical software. T-tests will be performed for continuous variables and Pearson's Chi-squared tests for categorical variables. Analysis will be tailored to compare B and O Supprenettes Suppositories and placebo/no suppository in order to best answer the research question.

1. Describe any new methodology and its advantage over existing methodologies.

There are no methodologies in this protocol which are new.

2. Discuss potential difficulties and limitations of the proposed procedures and alternative approaches to achieve the aims.

The procedure is designed so that patients receive a B and O suppository as they would as part of standard protocol in the post-operative period if bladder spasms were experienced. The only difference is regarding timing of administration. Therefore, there are no potential difficulties or limitations of the proposed procedure since B and O administration is already a well-accepted treatment for bladder spasms following urologic procedures.

3. Provide a tentative sequence or time table for the study.

November 2015 - IRB approval and begin recruiting patients for study

December 2015 - June 2016 Conducting study according to aforementioned protocol

July 2016 - Begin data analysis and manuscript preparation

4. Specify procedures, situations, or materials that may be hazardous to personnel and the precautions to be taken to ensure safety.

None

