5. Provide justification of the sampling procedure and sample size. Gender and Minority Inclusion, it is required that all research involving human subjects and human materials include minorities and women, as well as males and females of all ages. If one gender and/or minorities are excluded or are inadequately represented in a protocol, particularly in proposed population-based studies, a clear compelling rationale for exclusion or inadequate representation should be provided. The composition of the study population must be described in terms of gender and

racial/ethnic group, together with a rationale for its choice (by age distribution, risk factors, incidence/prevalence, etc.)

All participants undergoing lithotripsy procedures at GW hospital with the included physicians will be asked to participate in the study.

We determined the expected effect sizes based on previous studies of this same treatment in patients who received robot-assisted laparoscopic surgery for prostate CA.

Based on morphine equivalent dose in both Scavonetto, Lamborn, McCaffrey et al. (Can J. Urol 2013) and Lukaswycz, Holman, Kozlowski et al. (Can J Urol 2010), we would like to detect a 4 mg eq. difference between groups, with an expected standard deviation (sd) of 5, i.e., an effect size (d) of 0.8. For post-op pain rated on a 10-point scale both of the previous studies found sd ~2.0. We would like to detect a 1-point difference, so will power for an effect size of 0.5. Scavonetto et al. found approximately 20% of patients required use of rescue B&O suppositories and 60% requiring Oxybutynin for post-op bladder spasm. Thus, for this outcome we will try to detect a difference in percent positive of 20%. For all comparisons, we will use 2-tailed tests with alpha=.05.

Immediate post-op morphine equivalent dose.

In order to have power >.80 to detect an effect size of 0.8 in morphine eq. dose, we would need n=26 per group, or total N=51. For power >.90, we would need 34 per group or total N=68.

Post-op pain.

For an effect size of 0.5, in order to have power >.80, we would need 64 per group, or total N=128. For power >.90, we would need 86 per group, or total N=172.

Use of medication for bladder spasms.

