Here, we will want to detect a 20% difference between groups. Assuming that in the treatment group, 20% of patients need rescue medication for bladder spasm, while 40% need such meds in the control group, we would need n=82 per group (total N=164) in order to detect a difference this large with power >.80.

Therefore, in order to have adequate power across all 3 outcome measures, we plan to enroll a total of 180 subjects, randomized equally across treatment and control groups.

6. Identify all drugs and devices to be used, if applicable,. If the drug or device is investigational under FDA policy, list the actual IND/IDE number and respective source, supplier, and/or sponsor. If an IND/IDE has been assigned provide the FDA

stage status. Note the proposed dosage related information including instructions for administering, adverse effects, compatibility in infusions, and stability.

Please see package inserts for B and O suprette suppositories attached to this submission. We are also including Ditropan, which is the oral anti-muscarinic to be included in this study. The dosage of B&O will be 16.2mg/30mg which is in the formulary at GW. Ditropan will be given in the normal 5 mg dosage.

7. Identify all procedures that will be used for the purpose of this research. If blood is to be drawn, indicate amount to be withdrawn per single withdrawal, and the total amount of blood to be drawn. If transfusions are anticipated, include assurance that the volume of blood removed for research purposes will not necessitate a transfusion. [Refer to Section 1.5.5]

E. Study Population –(Gender and Minority Inclusions):

1. Describe the characteristics of the subject population, include the anticipated number of normal volunteers, age ranges, sex, ethnic background, and health status.

Identify the criteria for inclusion or exclusion (especially women and/or minorities).

Explain the rationale for the use of special classes of subjects, such as fetuses, pregnant women, or others who are likely to be vulnerable, especially those whose ability to give voluntary informed consent may be questionable.

The subject population will be patients seen at GW for lithotripsy procedures. This will include men and women ages 18-89. It will include all ethnic backgrounds, and anyone who has been cleared for surgery.

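### The 20% v 40% behind the rescue-medication sample size does not follow from the plan's own source, and power at the real group sizes is below 0.80 on several readings

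*Combined protocol and SAP*

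**What the plan says.** Section D, question 5 (sample size) says that expected effect sizes come from two earlier studies in robotic prostatectomy. For bladder-spasm medication it reports from one of them that "approximately 20% of patients required use of rescue B&O suppositories and 60% requiring Oxybutynin for post-op bladder spasm". It goes straight on: "Thus, for this outcome we will try to detect a difference in percent positive of 20" per cent.

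Under the heading on use of medication for bladder spasms, the calculation is then set up as "Assuming that in the treatment group, 20% of patients need rescue medication for bladder spasm, while 40% need such meds in the control group". The result is 82 per group, 164 in total, for power above 0.80. The section closes by saying that "in order to have adequate power across all 3 outcome measures, we plan to enroll a total of 180 subjects", allocated equally across treatment and control.

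The testing rules are "For all comparisons, we will use 2-tailed tests with alpha=.05" and, earlier in Section D, "T-tests will be performed for continuous variables and Pearson's Chi-squared tests for categorical variables".

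Procedural item 2 of Section D describes three randomised arms: control, postoperative suppository and preoperative suppository. On rescue, it says that "Patients in the postoperative and preoperative OR groups will be offered Ditropan for any bladder spasms in the post-operative setting". It also allows control patients a rescue suppository at the surgeon's discretion. Item 3 says that patients outside the experimental arm will receive oral antimuscarinics and no suppositories.

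**The concern.** The two assumed rates do not follow from the evidence offered for them. The source supplies 20% for one drug and 60% for another. The calculation uses 20% for treatment and 40% for control. The 20% equals the cited rescue-suppository rate, although the plan does not say that it comes from there. The 40% appears without a source or a derivation. Nor does a 20-point difference follow from the figures 20% and 60%.

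The outcome itself is not defined. Its heading covers medication for bladder spasms generally, and the active arms are offered Ditropan, the study's oral antimuscarinic (oxybutynin in Section G). For those arms the 60% is the more relevant of the two cited rates, yet it is not used.

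This matters because a fixed absolute difference needs more patients the closer the two rates lie to 50%. At power 0.80 this outcome also has the largest stated requirement of the three (82 per group, against 26 and 64), so the claim of adequate power on all three depends on it. That claim further treats 180 as two groups, while the design has three.

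**Working it through.** **Inputs.** From the plan: two-sided alpha 0.05, Pearson chi-squared, a 20-point difference, 20% v 40%, 82 per group, 180 in total and three arms. Power of 0.80 uses z = 0.8416; alpha uses z = 1.96.

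**Formulae.** With rates p1 and p2, mean p̄ and difference d = 0.20:

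- n per group = [1.96·√(2p̄(1−p̄)) + 0.8416·√(p1(1−p1) + p2(1−p2))]² / d²
- power = Φ{[d√n − 1.96·√(2p̄(1−p̄))] / √(p1(1−p1) + p2(1−p2))}

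**Reproducing the plan's figure (20% v 40%).** p̄ = 0.30, so √0.42 = 0.6481, and √(0.16 + 0.24) = 0.6325. Then n = (1.2702 + 0.5323)² / 0.04 = 81.2, rounded up to 82. Power at 82 is Φ(0.855) = 0.804. The plan's figure is confirmed.

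**If 60% is the control rate (40% v 60%).** p̄ = 0.50, so √0.50 = 0.7071, and √(0.24 + 0.24) = 0.6928. Then n = (1.3859 + 0.5831)² / 0.04 = 96.9, rounded up to 97, or 194 for two groups. Power at 82 is Φ[(1.8111 − 1.3859) / 0.6928] = Φ(0.614) = 0.730.

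**All readings, 20-point difference kept.** Group sizes are 82 (the plan's figure), 90 (180 in two groups) and 60 (180 in three arms). The last column pools both suppository arms against control, using p̄ weighted by group size.

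| Reading of the 60% | Treated v control | n per group for 0.80 | Power at 82 | Power at 90 | Power at 60 | 120 active v 60 control |
|---|---|---|---|---|---|---|
| Not used (plan's inputs) | 20% v 40% | 82 | 0.804 | 0.839 | 0.670 | 0.806 |
| Control rate | 40% v 60% | 97 | 0.730 | 0.770 | 0.593 | 0.721 |
| Average of two equal arms | 50% v 70% | 93 | 0.748 | 0.787 | 0.611 | 0.733 |
| Treated rate | 60% v 80% | 82 | 0.804 | 0.839 | 0.670 | 0.785 |

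**Pooled column, worked once (20% v 40%).** p̄ = (120 × 0.20 + 60 × 0.40) / 180 = 0.2667. The null standard error is √[0.2667 × 0.7333 × (1/60 + 1/120)] = 0.0699. The alternative standard error is √(0.24/60 + 0.16/120) = 0.0730. Power = Φ[(0.20 − 1.96 × 0.0699) / 0.0730] = 0.806.

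**Where power falls below 0.80.** At 82 per group, it does so for control rates of about 40.5% to 79.5%. At 90 per group, the interval is about 47% to 73%.

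**Check on the approximation.** Exact enumeration of the Pearson test gives 0.807 (20% v 40%, n = 82), 0.734, 0.756 and 0.612 (40% v 60%, n = 82, 90 and 60) and 0.684 (20% v 40%, n = 60). Each is within 2 points of the table, and none changes the conclusion.

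**The case against.** The strongest reply is that nothing has been miscalculated. The inputs are stated and 82 follows from them. That stands: the defect is an unsupported input, and a reader who inferred an arithmetic error would be wrong.

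A reader might also infer that 60% is the control rate, or that the stated power fails over most of the range the source implies. The documents do not support either. They give two point rates, with no arm, no combined rate and no range. If 60% is the treated rate, 82 per group still gives 0.804. The share of cases below 0.80 depends on the reading: 98% of control rates from 40% to 60%, but 49% of those from 20% to 60%. A 20% v 60% contrast would need only 23 per group, though the plan fixes the difference at 20 points.

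The cited rates come from prostatectomy. Section B says those studies did not cover lithotripsy, and Section G says that not every lithotripsy patient has spasms. A lower base rate is therefore possible. The plan does not argue for one.

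The shortfall is modest if 180 means two groups: at 90 per group the lowest power for a 20-point difference is 0.770. At 82 per group with a 60% control rate, a difference of 22 points gives 0.810. The loss at 60 per arm comes mostly from splitting 180 three ways and should be counted separately. Nor is it certain that this outcome set the 180, since the plan also gives a total of 172 for pain at power 0.90.

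Finally, Section D says that analysis will be tailored to compare suppository with placebo or no suppository, which could mean the pooled contrast. At the plan's own rates that contrast reaches 0.806. It falls short on all three readings of the 60%, and it cannot address the timing question raised in Section B.

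**Conclusion.** The point holds as an unsupported assumption with consequences for the stated power. The 82 per group is right for 20% v 40%, but that pair does not follow from the source the plan quotes. With the 20-point difference kept, power at 82 per group runs from 0.73 to 0.80 over the three readings of the 60%. At 90 per group it runs from 0.77 to 0.84, and at 60 per arm from 0.59 to 0.67. The first two readings, 60% as the control rate or as the average, miss 0.80 even at 90 per group. The third does not.

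Independently of the base rate, three equal arms give 180 / 3 = 60 per arm and pairwise power of 0.67 at the plan's own rates. Sixty is also below the 64 per group that the plan gives for pain at power above 0.80. The claim of adequate power on all three outcomes therefore cannot stand unqualified.

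These figures assume a two-sided 0.05 test without continuity correction or multiplicity adjustment, and complete data. Which reading of the 60% applies cannot be settled from the documents.

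**What to change.** - Define the outcome: rescue suppository, oxybutynin, or either.
- State which arm or arms the cited 20% and 60% come from, and justify any control rate that departs from them.
- Replace the single 82-per-group figure with power at the actual group sizes, for control rates of 40% to 80% with a 20-point difference, including 40% v 60%. Say whether the comparison is pairwise (60 v 60) or pooled (120 v 60).
- Withdraw or qualify the claim of adequate power on all three outcomes.
- Reconcile items 2 and 3 of Section D on suppositories for control patients, because they determine what counts as rescue medication in that arm.

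The cost is revised text and a stated power that looks less favourable. No extra enrolment is needed.

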## RESEARCH PLAN

### A. Specific Aims

List the broad, long-term objectives and describe concisely and realistically what the specific research described in your proposal is intended to accomplish, and the hypothesis to be tested.

The long-term objectives of the study are to determine whether earlier administration of Belladonna and opium (B and O) suppositories ameliorates the discomfort associated with bladder spasms and reduces the need for oral narcotics and antimuscarinics in the post-operative setting.

Most patients who receive B and O suppositories in the post-operative period receive them in the PACU after expressing discomfort. The administration of B and O suppositories in these cases can often be hours from surgery end time.

The hypothesis to be tested is that giving patients B and O suppositories prior to surgery or post-operatively while still in the operating room will reduce the amount of pain medications that people will need post-operatively, reduce the amount of discomfort that patients experience from bladder spasms, and possibly reduce the length of hospital stay.

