### B. Background and Significance

Briefly give the background to the present proposal, critically evaluate existing knowledge, and specifically identify the gaps which the project is intended to fill. Cite literature and include a list of references.

Bladder Spasms are a frequent cause of discomfort in the post-operative setting after lithotripsy, and while B and O suppositories are occasionally used post-operatively to relieve bladder spasms, there are no studies that show how effective they are. There are two studies that evaluated the use of B and O suppositories in a perioperative setting after robotic prostatectomies:

Lukasewycz S, Holman M, Kozlowski P, Porter CR, Odom E, Bernards C, Neil N, Corman JM. Does a perioperative belladonna and opium suppository improve postoperative pain following robotic assisted laparoscopic radical prostatectomy?

Results of a single institution randomized study. *Can J Urol.* 2010 Oct;17(5):5377-82. PubMed PMID: 20974030

These two studies show a possible benefit to perioperative belladonna and opium suppositories. However, these studies have never evaluated the use of the suppositories in lithotripsy procedures where the bladder is dilated and drained multiple times during a procedure. The constant distension leads to bladder spasms in the post-operative setting, which require narcotics and anti-muscarinics. There are also no studies to evaluate the effect of timing of administration of these suppositories in lithotripsy cases on postoperative pain, the use of narcotics in the post-operative period, and length of hospital stay.

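### The sample size is calculated for two equal groups, but the trial has three arms of about 60, so the claim of adequate power on all three outcomes holds only if the two B and O arms are pooled

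*Combined protocol and SAP*

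**What the plan says.** Section D.5 of the combined protocol and SAP gives a two-group sample size for each of three outcomes. For power above .80 these are 26 per group for morphine-equivalent dose, 64 per group (128 in all) for pain, and 82 per group (164 in all) for use of spasm medication. On error rate it says "For all comparisons, we will use 2-tailed tests with alpha=.05". It concludes that "in order to have adequate power across all 3 outcome measures, we plan to enroll a total of 180 subjects". The same sentence then describes the allocation of these patients as "randomized equally across treatment and control groups".

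Section D, item 2, describes a different layout: "The patients will be divided into three research arms", namely control, postoperative OR and preoperative OR. On allocation it says: "Patients will be randomly selected for one of the groups using a random number generator between 1 and 3".

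Three other places bear on which comparison is meant:

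- The data-analysis paragraph of Section D: "Analysis will be tailored to compare B and O Supprenettes Suppositories and placebo/no suppository".
- The hypothesis in Section A, which joins the two timings: "giving patients B and O suppositories prior to surgery or post-operatively while still in the operating room".
- Section B, which lists timing as a gap in the evidence: "no studies to evaluate the effect of timing of administration of these suppositories in lithotripsy cases".

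**The concern.** Each total in D.5 is about twice its per-group size, and no third arm appears in the calculation. Split three ways, 180 patients give 180/3 = 60 per arm, which is below two of D.5's own three per-group sizes.

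A reader therefore cannot tell which comparison the power above .80 covers. If a single B and O arm is compared with control and the result on spasm medication is not significant, D.5 would let it pass as an adequately powered negative, although a true difference of the planned size would be missed about one time in three. A comparison of preoperative with postoperative administration would also be about 60 vs 60, and the documents plan no difference for it.

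**Working it through.** **Inputs, all from D.5 unless stated.** Two-sided alpha .05. Morphine dose: difference 4, SD 5, d = 0.8. Pain: difference 1, SD 2, d = 0.5. Spasm medication: 40% control, 20% treated. N = 180. Three arms with equal chance (Section D, item 2). Tests are the t-test and Pearson's chi-squared (Section D, data analysis).

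**Formulas.** Means: noncentral t with n1 + n2 − 2 degrees of freedom and noncentrality d·√(n1·n2/(n1+n2)). Proportions: power = Φ[(|pC − pT| − 1.96·s0)/s1], where s0 = √(p̄(1−p̄)(1/nC + 1/nT)), s1 = √(pC(1−pC)/nC + pT(1−pT)/nT), and p̄ is the weighted mean rate. Exact figures are the exact binomial power of the uncorrected chi-squared test.

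**Step 1: reproduce D.5.** The per-group sizes are right for two equal groups: 26 vs 26 gives 0.807, 64 vs 64 gives 0.801, and 82 vs 82 gives 0.804 (81 vs 81 gives 0.799).

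**Step 2: one B and O arm vs control, 60 vs 60.**

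- Pain: noncentrality 0.5·√30 = 2.739, 118 df, power 0.775.
- Morphine dose: noncentrality 0.8·√30 = 4.382, power 0.991.
- Spasm medication: p̄ = 0.30; s0 = √(0.21·2/60) = 0.0837; s1 = √((0.24+0.16)/60) = 0.0816; (0.20 − 1.96·0.0837)/0.0816 = 0.441; power Φ(0.441) = 0.670.

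**Step 3: both B and O arms pooled vs control, 120 vs 60.**

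- Pain: noncentrality 0.5·√40 = 3.162, 178 df, power 0.882.
- Morphine dose: noncentrality 0.8·√40 = 5.060, power 0.999.
- Spasm medication: p̄ = (60·0.40 + 120·0.20)/180 = 0.2667; s0 = 0.0699; s1 = √(0.24/60 + 0.16/120) = 0.0730; (0.20 − 1.96·0.0699)/0.0730 = 0.862; power Φ(0.862) = 0.806.

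| Contrast | Morphine dose | Pain | Spasm medication (exact) |
|---|---|---|---|
| One arm vs control, 60 vs 60 | 0.991 | 0.775 | 0.670 (0.684) |
| Pooled B and O vs control, 120 vs 60 | 0.999 | 0.882 | 0.806 (0.813) |
| Two equal groups, 90 vs 90 | >0.999 | 0.916 | 0.839 (0.842) |

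**Step 4: size of the single-arm shortfall.** With 60 vs 60, 80% power is reached at d = 0.516 for pain, that is 0.516·2 = 1.03 points against the planned 1.0. For spasm medication it is reached at 40% vs 17.1%, a difference of 22.9 percentage points against the planned 20.

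**Step 5: margin of the pooled contrast.** Two equal groups need 164 of the 180 patients for spasm medication, leaving 16 spare. At 2:1, 59 vs 118 (N = 177) gives 0.799, so all 180 are needed; by exact power 177 suffice (0.805). Pain needs 144 at 2:1. The 1-to-3 draw does not fix arm sizes: the control arm has a central 95% range of 48 to 73, over which pooled spasm-medication power runs from 0.763 to 0.831. Its mean is 0.803 (exact 0.806), and the chance that it falls below .80 is 35% (exact 29%), mostly by a small amount.

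**The case against.** The strongest reply is that nothing in D.5 is miscalculated and that the only analysis text compares B and O with no suppository. With the joint hypothesis in Section A, that implies pooling, and for the pooled contrast the claim is true. No section designates a single arm vs control as a planned test, and 0.775 for pain is an immaterial miss. This is fair as far as it goes: the pain shortfall is small, and pooling is the better-supported reading. But no section states the pooling, the analysis paragraph leaves the comparison to be tailored, timing is named as a gap, and D.5 calculates for group sizes that the trial will not have.

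Three further points refine the conclusion.

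- Pooled power assumes that both timings reach the full planned effect. As an illustration not taken from the documents, rates of 20% and 30% in the two B and O arms average 25%, and pooled power for spasm medication falls to 0.54; with 20% and 25% it is 0.68.
- The assumed rates matter as well: at 60% vs 40%, also a 20-point difference, pooled power is 0.72.
- The equal-allocation wording could be read as 90 vs 90, which would meet every target, but that conflicts with the 1-to-3 draw. It can also mean three groups of 60, so it needs clarifying rather than counting as a separate error.

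**Conclusion.** The concern holds and should be fixed. As written, the claim of adequate power on all three outcomes is not true of a single B and O arm against control: spasm medication is clearly short (0.67, so a real effect is missed about 33% of the time), pain is marginally short (0.78, missed about 22%), and morphine dose is well powered (0.99). The claim is true of pooled B and O against control, but with almost no margin on spasm medication.

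These figures rest on D.5's own differences, SDs and alpha, on 60 patients per arm, on no losses, and, for the pooled contrast, on both B and O arms sharing the planned effect. The documents give no loss rate; medication use is taken from charts at 24 hours, so losses on that outcome may be few.

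**What to change.** Keep N = 180 and revise D.5 as follows:

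1. State that there are three arms of about 60 each, and reword the equal-allocation phrase to match.
2. Name pooled B and O (about 120) vs control (about 60) as the powered contrast, before any analysis.
3. Give its power as more than .99 (morphine dose), .88 (pain) and about .81 (spasm medication), assuming 60 controls, no losses and the planned effect in both B and O arms. Say that the last figure has almost no margin.
4. Limit the adequate-power sentence to that contrast.
5. State that power for one B and O arm vs control is .99, .78 and .67, and that preoperative vs postoperative power is the same only if the same differences are assumed, since none is planned.

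This costs wording only and no extra patients. The price is an open statement that single-arm comparisons fall below .80 for spasm medication and, marginally, for pain. If the sponsor wants arm-level comparisons powered instead, D.5's per-group sizes imply 3 × 64 = 192 patients for pain or 3 × 82 = 246 for spasm medication.
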